3. EXPECTED RISKS AND BENEFITS

Reported complications rates in Endothelial Keratoplasty are low. DM is expected to be associated with comparable complication rates. Complications may occur either intra-operatively or post-operatively¹:

Intra-operative complications:

- Incomplete stripping of host Descemet's Membrane (DM): 1.6%
- Air bubble-related problem: 1.3%
- Scoring and stripping of host DM not possible: 0.9%
- Reverse-unfolding of donor DM: 0.5%
- Inadvertent expulsion of donor button from anterior chamber: 0.2%

Post-operative complications:

- Donor graft dislocation: 4.9%
- Air-bubbled induced pupillary block glaucoma: 2.8%

- Secondary glaucoma: 1.6%
- Partial donor graft detachment: 0.7%
- Delayed visual rehabilitation from primary failure 5%
- Blood in graft interface: 0.5%
- Bacterial endophthalmitis: 0.2%

Benefits:

- Endothelial keratoplasty is currently the standard of care for the management of advanced Fuchs' Endothelial Dystrophy
- The patient may benefit since the endothelial recovery will be from their own cells and not donor cell, hence there will no risk of rejection
- Since the cell will be from the patients own, the long term endothelial cell attrition seen in current endothelial keratoplasty techniques will not occur
- Since the cells will be from the patients own there will be no need to use prolonged topical immunosuppression and hence avoid the risk of steroid related complications e.g. glaucoma
- The patient's participation will contribute to the medical knowledge about the use of DM transplant for the treatment of Fuchs' Endothelial Dystrophy.

Risks

- The endothelial recovery may be prolonged – if this occurs then the patient will be given the option to undergo a conventional endothelial keratoplasty

References

4. STUDY POPULATION

4.1. Number and nature of subjects to be enrolled.

Patients will be recruited at Singapore National Eye Centre. The study will be a prospective, open label clinical trial where **20 patients** will be selected to undergo DM transplant for the treatment of Fuchs' Endothelial Dystrophy (FED).

The patient population for this study is patients with FED. Our previous ex vivo study has shown that older patients (>65 years old) are less likely to respond favourably to DM transplant alone and data from reported clinical cases of DM stripping alone have shown that endothelial recovery was only achievable in 50% of the cases over the age of 65 years old. Hence, an age range of <65 years old is set for this study. To include age range >65 to 85 as well, Rho kinase inhibitor eye drops will be prescribed to patients with age higher than 65 years old. 10 patients age between 65 to 85 will be recruited for DM transplant coupled with Rho kinase inhibitor. No racial, minority or gender exclusion criteria will be applied.

4.2. Criteria for Recruitment and Recruitment Process

Patients with Fuchs' Endothelial Dystrophy who are interested in participating and have provided informed consent will be examined preoperatively by the principal investigator (A/[name] [name]). Baseline measurements to assess eligibility will include age, slit lamp assessment, slit lamp photography, intraocular pressure, specular microscopy, ultrasound corneal pachymetry, Pentacam scan, best corrected visual acuity, contrast sensitivity and anterior segment colour photography. These tests will be performed by certified ophthalmic imaging technicians and Singapore Nursing Board registered staff nurses employed by the Singapore National Eye Centre. A random venous blood sample will also be obtained from each patient and subject to genetic analysis for the presence of the CTG18.1 repeat expansion. Venepuncture will be performed by a Singapore Nursing Board registered staff nurse employed by the Singapore National Eye Centre.

The decision for eligibility for recruitment into the study will be made by the principal investigator (A/[name] [name]), based on results of the pre-operative assessment. Informed consent and pre-operative counselling will be administered by a specialized research coordinator employed by the Singapore National Eye centre / Singapore Eye Research Institute. The principal investigator (A/[name] [name]) will be available to provide clarifications and explanations if requested by the participant or research coordinator.

4.3. Inclusion Criteria

1. Fuchs' Endothelial Dystrophy (FED) as defined by any of the following criteria:
 - a. FED of at least Grade 4 on the Krachmer grading scale (i.e. greater than 5mm of confluent central corneal guttata)
 - b. Best-corrected-visual-acuity of less than 6/12 in a patient clinically diagnosed with FED of any grade, in which poor visual acuity cannot be accounted by any other significant ophthalmic disease (e.g. cataracts, age-related macular degeneration, glaucoma, optic neuropathies)
2. Patients in the range of <85 years old will be recruited for this study
3. Only individuals with the mental capacity to provide informed consent will be included.
4. Patients who are willing and able to sign a written Informed Consent Form prior to any study-specific procedures will be included
5. Patients who are willing and able to return for scheduled follow-up examinations for up to 12 months after the surgery will be included

4.4. Exclusion Criteria

Subjects that meet any of the following criteria will be excluded from participation:

1. Eyes which have previously been subject to any form of keratoplasty
2. An only-functioning eye in a patient who has lost visual potential in the contralateral eye
3. Patients with chronic, advanced FED who meet the above mentioned inclusion criteria, but whose disease is associated with significant stromal scarring to such an extent that will predictably impair post-operative visual recovery after DSAEK or DM transplant
4. Patients whose corneal endothelial disease may possibly be attributed to pathologies

other than FED, including but not limited to pseudophakic bullous keratopathy, laser-peripheral-iridotomy induced bullous keratopathy, iridocorneal endothelial syndrome, Axenfeld Rieger syndrome, congenital hereditary endothelial dystrophy and any other anterior segment developmental anomalies

5. Patients with visually significant cataracts
6. Patients with diagnosed with visually significant retinal disease, including but not limited to age-related macular degeneration, myopic macular degeneration, diabetic retinopathy, diabetes related maculopathy, retinal vein occlusion related maculopathy, retinal dystrophies and previous retinal detachments.
7. Patients with any form of glaucoma
8. Patients diagnosed with visually significant, non-glaucomatous optic neuropathies, including but not limited to those related to ischemic (both arteritic and non-arteritic), toxic, nutritional, myopic, compression, infective and inflammatory causes
9. Patients who are pregnant, lactating, of child-bearing potential and not practising a medically approved method of birth control, or planning to become pregnant during the course of the trial, and patients with other conditions associated with fluctuation of hormones that could lead to refractive changes.

5. STUDY DESIGN AND PROCEDURES/METHODOLOGY

Study Design

This is prospective, open non-randomized clinical trial. Eligible patients who fit our recruitment criteria and who are interested in surgery for improvement of symptoms related to FED will be informed of the availability of this study at the Singapore National Eye Centre. They will first be counselled on the procedures involved in conventional endothelial keratoplasty, which is the current standard of care, together with a discussion on the risks and benefits associated with endothelial keratoplasty. They will subsequently be presented with the alternative option of DM transplant, with a full explanation detailing the experimental nature of this approach, together with a discussion on the potential risks and benefits of DM transplant vis-à-vis conventional endothelial keratoplasty. They will also be counselled regarding the possibility of subsequently undergoing a rescue endothelial keratoplasty procedure in the post-operative period, should there be evidence suggesting that there is prolonged visual recovery following DM transplantation. Patients will be informed of the potential risks and benefits of the rescue endothelial keratoplasty. After provisional consent, patients will be screened for inclusion and exclusion criteria (listed above). Patients that meet the eligibility criteria will be consented and assigned to undergo DM transplant in the eye that has the more severely affected by FED. We aim to recruit a total of **20** patients for this study.

Graft Preparation

Donor corneas will be supplied by the Singapore Eye Bank. A 5-6mm Descemet's membrane graft will be prepared from the corneal button. Endothelial cells will be removed by simple wiping with a spear and removal of endothelial cells will be confirmed by trypan blue staining. All preparation will be performed by the principal investigator (A/[name] [name]), with the assistance of accredited technicians at the Singapore Eye Bank.

Surgical Procedure

All DM transplant procedures will be performed at the Singapore National Eye Centre (SNEC) by a fully qualified corneal surgeon (A/[name] [name], Head of the corneal service) who regularly performs and teaches endothelial keratoplasty. The surgical procedure will involve 1) Corneal incision, 2) Stripping of the central 5-6mm diameter of host diseased Descemet's membrane and endothelium, 3) Insertion of donor Descemet's roll, 4) Unscrolling of Descemet's membrane graft and positioning onto the posterior corneal surface by an expansile gas bubble (20% Sulphur Hexafluoride, SF₆), 5) Creation of an inferior peripheral iridotomy, and 6) Closure of corneal incision with 10-0 nylon sutures.

Post-operative Care

All patients will be prescribed topical antibiotics and steroidal eyedrops post-operatively. For patients above the age of 65, an additional Rho kinase inhibitor eyedrop will be prescribed to the patient. They will be reviewed by the surgeon (A/[name] [name]) immediately after the procedure, at post-operative day 1, week 1, week 3, week 6, week 12, week 24 and week 48. Additional visits may be scheduled as required.

Primary outcomes

Measurements of best-corrected-visual-acuity, central endothelial cell count and corneal pachymetry will be obtained every month, starting from post-operative month 1. These measurements will be made by certified ophthalmic imaging technicians and Singapore Nursing Board registered staff nurses employed by the Singapore National Eye Centre.

Other outcome Measurements

1. Slit lamp examination every visit to visualize graft position and corneal hydration status
2. Intraocular measurement with Goldmann applanation tonometry every visit
3. Anterior segment optical coherence tomography (ASOCT): Non-invasive non-contact measurement with Optical Coherence Topography, Visante (day 0, day 1, week 1, month 1 and month 12)
4. Pentacam scan: Non-invasive non-contact scan with OCULUS Pentacam (day 0, month 3 and month 12)
5. Documentation of any postoperative complications including but not limited to wound leak, graft dislocation, partial graft detachment, SF₆-bubble induced pupillary block glaucoma, iris damage and bacterial endophthalmitis

All measurements will be made by the principal investigator (A/[name] [name]), certified ophthalmic imaging technicians and Singapore Nursing Board registered staff nurses employed by the Singapore National Eye Centre.

Rescue Endothelial Keratoplasty

Post-operatively, patients who have undergone DM transplant will be clinically assessed by the surgeon (A/[name] [name]) during each post-operative visit. Prolonged visual recovery defined as clinical outcomes which are significantly worse than what would be expected following conventional endothelial keratoplasty for the treatment of FED in an equivalent patient i.e no improvement in visual acuity by 6 weeks. A patient who demonstrates poor recovery, or non-recovery, may be counselled on the need for rescue

conventional endothelial keratoplasty procedure, as determined by the surgeon ([name]). The patient will be advised on the procedures involved, and the associated risks and benefits. Patients who consent to rescue endothelial keratoplasty will undergo standard Descemet's Stripping Automated Endothelial Keratoplasty (DSAEK) performed by the surgeon (A/[name] [name]) at the earliest possible date.

Data Collection and Storage

The surgical procedure will be recorded on a DVD. The DVD will be stored in a locked cupboard and retained for 15 years; it will be put in long-term storage afterwards. All the data from imaging procedures will be stored on password-protected devices at Singapore National Eye Centre. All other clinical examination data will be entered and stored in confidential patient dossiers maintained by the Medical Records Office of the Singapore National Eye Centre at a secure location within the Centre. Data and samples may be de-identified and used for future studies. Where required, such future studies will be submitted for review and necessary approval by the relevant institutional review board.

Withdrawal

Subjects may withdraw voluntarily from participation in the study at any time. If they withdraw from the study after consenting but prior to surgery, no specific arrangements for follow-up or special care are required. If they withdraw from the study in the follow-up period, after having surgery, they will be advised to continue the regular scheduled follow-up for safety reasons. If a patient withdraws from the study due to the development of a complication, appropriate follow-up will be arranged until the symptoms of the adverse event resolve and the subject's condition becomes stable.

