13. RETENTION OF STUDY DOCUMENTS

Records for all participants, including CRFs, all source documentation (containing evidence to study eligibility, history and physical findings, laboratory data, results of consultations, etc.) as well as IRB records and other regulatory documentation will be retained by the PI in a secure storage facility. The records will be accessible for inspection and copying by authorized authorities. Study documents will be kept by SERI for 15 years, and then destroyed.

14. FUNDING and INSURANCE

This study is department supported.

The cost of Descemet Membrane Transplantation surgery and genetic analysis of CTG trinucleotide repeats will be absorbed by the department. Participants will pay for all other costs including all pre- and post-operative follow-up visits, and all relevant investigations performed. The clinical visit schedule and investigations required are identical to patients undergoing standard endothelial keratoplasty, thus participants will not be required to pay more than what is expected for standard endothelial keratoplasty.

Should a complication occur, the follow-up treatment will be to perform a standard endothelial keratoplasty, and the participant will be expected to bear the cost of this surgery i.e. such a participant will pay the same surgical fees as a conventional patient who decides to undergo standard endothelial keratoplasty for treatment of Fuchs Endothelial Dystrophy.

Singapore National Eye Centre and Singapore Health Services do not make any provisions to compensate study participants for research related injury or complications. However, compensation may be considered on a case-by-case basis for unexpected complications and injuries due to non-negligent causes.

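### Do the monthly primary measurements fail because the list of surgeon reviews has too few visits to carry them?

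*Combined protocol and SAP*

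**What the plan says.** Section 5 of the combined protocol and SAP holds three timing statements.

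- **Primary outcomes:** "Measurements of best-corrected-visual-acuity, central endothelial cell count and corneal pachymetry will be obtained every month, starting from post-operative month 1". No last month is given. On who does the work: "These measurements will be made by certified ophthalmic imaging technicians and Singapore Nursing Board registered staff nurses".
- **Post-operative Care:** the surgeon reviews the patient straight after the operation and then "at post-operative day 1, week 1, week 3, week 6, week 12, week 24 and week 48". The paragraph ends: "Additional visits may be scheduled as required".
- **Other outcome Measurements:** anterior segment OCT at "day 0, day 1, week 1, month 1 and month 12", and the Pentacam scan at day 0, month 3 and month 12.

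Three other sections bear on the point. Section 4.3 requires patients to be willing and able to "return for scheduled follow-up examinations for up to 12 months after the surgery". Section 6.3 has efficacy assessed every three months. Section 14 says: "The clinical visit schedule and investigations required are identical to patients undergoing standard endothelial keratoplasty". No section converts weeks to months or sets visit windows.

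**The concern.** The primary outcomes are due monthly, but no monthly visits are listed. Reviews are counted in weeks, while the primary measurements and later imaging are counted in months. Speed of recovery is part of the primary aim and of secondary aim 2 (section 2), and it can be seen only as finely as visual acuity, cell count and pachymetry are measured. If clinic appointments came from the review list alone, more than half of the monthly measurements would never be taken, and no analysis could recover them. Recovery after week 12 could then be dated only to the interval between weeks 12 and 24, or between weeks 24 and 48.

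The unstated month length adds a second worry. Week 48 may or may not be month 12, when OCT and Pentacam are due.

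**Working it through.** The plan states no number of monthly measurements, so there is no figure to reproduce. The check is a count, followed by a comparison of the texts.

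**Inputs.** Monthly measurement from month 1 (section 5, Primary outcomes). Reviews on the day of surgery, at day 1 and at weeks 1, 3, 6, 12, 24 and 48 (section 5, Post-operative Care). End at month 12, which is an assumption drawn from the follow-up period in section 4.3. Month length is also an assumption: 4 weeks, or a calendar month of 365.25 / 12 / 7 = 4.348 weeks.

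**Lower bound.** Reviews after week 1 number 5. If each serves at most one month, 12 - 5 = 7 months have none. If calendar-month measurement stopped at week 48, then 48 / 4.348 = 11.04, so 11 months fit and 11 - 5 = 6 have none.

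**Sensitivity, months 1 to 12 without a listed review:**

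| Rule for matching a review to a month | 4-week month | Calendar month |
|---|---|---|
| Same day | 9 | 12 |
| Within 7 days | 8 | 11 |
| Within 14 days | 7 | 9 |
| Any review inside the month | 7 | 7 |

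So 7 is the minimum for the surgeon reviews. Counting the separate month-12 imaging as an attendance can bring it to 6: weeks 3, 6, 12, 24 and 48 serve months 1, 2, 3, 6 and 11, and imaging serves month 12.

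**Spacing if only the list were used.** 24 - 12 = 12 weeks, then 48 - 24 = 24 weeks. Before that, reviews at weeks 3, 6 and 12 lie 3 and 6 weeks apart.

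**Month length.** On 4-week months, weeks 12, 24 and 48 are exactly months 3, 6 and 12 (12/4, 24/4, 48/4), in line with Pentacam at month 3 and imaging at month 12. On calendar months, month 12 is week 12 x 4.348 = 52.2, which is 52.2 - 48 = 4.2 weeks after the last listed review. The month-1 OCT (week 4.0 or 4.3) lies between the week-3 and week-6 reviews on either definition. Imaging is therefore not confined to the review days.

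**The texts side by side.** The week list fixes when the surgeon sees the patient. The monthly sentence fixes when technicians and nurses take the three primary measurements. Neither refers to the other, and neither says that measurements are limited to review days. Both can be met at once: the reviews as listed, plus measurement attendances in the other months, which the sentence on additional visits permits.

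**What a rewrite would gain.** Listing the monthly sessions would add no measurement, since they are already required. Cutting measurement back to the listed reviews would give 5 per eye in place of 12 and would discard planned data. A window of 2 weeks either side would also be flawed. On 4-week months, month 1 (day 28) and month 2 (day 56) would share day 28 + 14 = 56 - 14 = 42, which is the week-6 review.

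**The case for a change.** The strongest case for a change is that a required primary measurement should not depend on visits left to discretion. As-required visits may be prompted by how the eye is doing, so measurement times could become tied to outcome. Section 5 attaches only slit-lamp examination and tonometry to every visit, so even the five reviews carry the primary measures by inference. Under section 14 participants pay for follow-up visits and investigations, so the number of sessions affects them, and the schedule is said to match that for standard endothelial keratoplasty. Section 6.3 adds a third interval for efficacy, and section 8.2 ties interim analyses to three-month follow-up. One calendar would be cheap.

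Part of this stands. The last month, month length, windows and session list are not stated, and a single calendar would be tidier. The rest does not show an error. Monthly measurement is a fixed rule in the plan, so the measurements themselves are not discretionary; only the booking of attendances is left open. The documents do not give the standard keratoplasty schedule, so section 14 cannot show an inconsistency. The three-monthly efficacy assessment may mean review of accumulated data. Monthly review of serious adverse events (section 6.3) and monthly safety analysis (section 8.2) are consistent with monthly contact, though they do not prove it.

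**Conclusion.** No change to the plan is needed. The count is right: with measurement to month 12, at least 7 of 12 monthly measurements fall outside the surgeon-review list, and between 7 and 12 do so depending on month length and window. The count compares two schedules with different purposes, and it does not show that any measurement would be missed. That loss requires the added premise that appointments are booked only from the review list.

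Even on that premise, the reviews at weeks 3, 6 and 12 cover early recovery, and weeks 24 and 48 would still show its extent. The cost would be coarser dating after week 12, in a study of 20 patients that section 8.1 calls exploratory.

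The conclusion rests on two assumptions: that the site follows the monthly rule as written, and that each measurement's date is recorded. With dates, the analyst can place results by time since surgery and need not settle whether a month is 4 weeks or a calendar month. The remaining detail belongs in the site's working calendar.

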6. SAFETY MEASUREMENTS

6.1. Definitions

An adverse event (AE) is any untoward medical occurrence in a patient or clinical investigation subject administered a pharmaceutical product and which does not necessarily have a causal relationship with this treatment.

A serious adverse event (SAE) or reaction is any untoward medical occurrence that at any dose:

- results in death
- is life-threatening
- requires inpatient hospitalisation or prolongation of existing hospitalisation
- results in persistent or significant disability/incapacity or
- is a congenital anomaly/birth defect
- is a medical event that may jeopardize the patient and may require medical or surgical intervention to prevent one of the outcomes listed above.

6.2. Collecting, Recording and Reporting of Adverse Events and Serious Adverse Events to CIRB

All adverse events will be reported via submission of the completed SAE Reporting Form to the approving CIRB, by the PI, within the timeframe defined below. The PI will also be responsible for informing the institution representative (local SAE resulting in death), sponsor or regulatory bodies as required and appropriate.

Reporting timeline to CIRB:

- SAE that result in death, regardless of causality, will be reported immediately – within 24 hours of the PI becoming aware of the event.
- Local life-threatening (unexpected/ expected) SAE will be reported no later than 7 calendar days after the PI is aware of the event, followed by a complete report within 8 additional calendar days.
- Local unexpected SAE that are related events, but not life-threatening, will be reported no later than 15 calendar days after the PI is aware of the event.
- An increase in the rate of occurrence of local expected SAE, which is judged to be clinically important, will be reported within 15 calendar days after the PI is aware of the event.
- Local expected SAE will be reported annually (together with Study Status Report for annual review).
- Local unexpected and unlikely related SAE that are not life-threatening will also be reported annually (together with Study Status Report for annual review).
- Local unexpected AE that are related events will be reported at least annually (together with Study Status Report for annual review).
- Non-local unexpected SAE that are fatal or life threatening and definitely/probably/possibly related will be reported not later than 30 calendar days after the PI is aware of the event.

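### Neither the adverse-event definition nor the complication outcome clearly requires non-serious intra-operative complications to be recorded, although section 3 lists five of them with rates

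*Combined protocol and SAP*

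**What the plan says.** Four parts of the combined protocol and SAP bear on this.

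- **Section 6.1, adverse event.** "An adverse event (AE) is any untoward medical occurrence in a patient or clinical investigation subject administered a pharmaceutical product". No causal link is needed and no start time is given. Surgery, procedure and graft are not mentioned.
- **Section 6.1, serious adverse event.** "A serious adverse event (SAE) or reaction is any untoward medical occurrence that at any dose" meets one of the listed criteria. One criterion is that the event "is a medical event that may jeopardize the patient and may require medical or surgical intervention to prevent one of the outcomes listed above". The reference to dose is drug language, but this definition is not limited to subjects given a drug.
- **Section 5, other outcome measurements, item 5.** "Documentation of any postoperative complications including but not limited to wound leak, graft dislocation, partial graft detachment", followed by further examples that include iris damage.
- **Section 3.** "Complications may occur either intra-operatively or post-operatively". Five intra-operative complications follow, with rates, and the protocol expects DM transplant to have rates comparable with endothelial keratoplasty.

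On the timing of drugs, section 5 states: "All patients will be prescribed topical antibiotics and steroidal eyedrops post-operatively". It adds: "For patients above the age of 65, an additional Rho kinase inhibitor eyedrop will be prescribed to the patient". Section 5 also provides for a DVD recording of each operation, and section 8.2 for a monthly analysis of safety data. Neither says which intra-operative data are to be extracted or analysed.

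**The concern.** The treatment being tested is an operation: host membrane is stripped, a donor membrane is inserted and unscrolled, and gas holds it in place. The adverse-event definition does not refer to any of this, and the eyedrops named for the patients come afterwards. In item 5, the open-ended wording widens the types of event but leaves the time window post-operative. A complication that arises and is resolved on the table, without meeting a seriousness criterion, therefore has no clear place in the safety data.

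Section 8.1 describes the study as exploratory and first-in-man. How often stripping, insertion or unscrolling goes wrong is basic information from the first 20 cases. If recording depends on how each reader interprets 6.1, a low intra-operative count could reflect either a smooth procedure or incomplete capture, and the report could not tell the two apart.

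**Working it through.** The plan gives no figure of its own on this point. The check has two parts: which rule captures which event, and how likely such an event is on the plan's own rates.

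**Which rule captures which event**

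| Event during surgery | 6.1 adverse event | 6.1 serious adverse event | Section 5, item 5 |
|---|---|---|---|
| Meets a seriousness criterion | Unclear | Yes | Only if it is also a post-operative complication |
| Not serious, leaves effects visible later (e.g. iris damage) | Unclear | No | Yes, through those effects |
| Not serious, resolved during surgery | Unclear | No | No |

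The last row is the gap. No outcome, safety or analysis section closes it.

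**Inputs** (section 3, intra-operative list)

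- Incomplete stripping of host membrane: 1.6%
- Air-bubble problem: 1.3%
- Scoring and stripping not possible: 0.9%
- Reverse unfolding of the donor membrane: 0.5%
- Expulsion of the donor button: 0.2%
- Number of operations: 20 (section 8.1; one eye per patient under section 5)

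Section 3 does not say whether one operation can count in several categories, so the rate *p* of operations with at least one of the five is bracketed.

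**Formulas.** Expected number = 20 × *p*. P(at least one) = 1 − (1 − *p*)^20.

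- No overlap: *p* = 1.6 + 1.3 + 0.9 + 0.5 + 0.2 = 4.5%. Expected number = 20 × 0.045 = 0.9. P = 1 − 0.955^20 = 60.2%.
- Independent categories: *p* = 1 − 0.984 × 0.987 × 0.991 × 0.995 × 0.998 = 4.43%. P = 59.6%.
- Full overlap: *p* is the largest single rate, 1.6%. Expected number = 20 × 0.016 = 0.32. P = 1 − 0.984^20 = 27.6%.

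The range is about 28% to 60%. It covers events of any seriousness. The documents do not give the non-serious share, so the chance of an event in the last row of the table cannot be calculated; it is at most 60%.

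**Precision with 20 operations.** If none is seen, the upper limit of the two-sided exact 95% interval is 1 − 0.025^(1/20) = 16.8%. This is well above the 4.5% benchmark.

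**The case against.** The strongest reply is that 6.1 is loosely drafted rather than exclusionary. Several points support it.

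- The serious-adverse-event definition is not tied to a drug, so serious intra-operative events are reportable. This stands.
- The withdrawal paragraph in section 5 treats a complication as an adverse event, which suggests that the authors meant the term broadly. This stands as evidence of intent, but it does not instruct anyone to record intra-operative events.
- Every patient is prescribed eyedrops and SF6 gas is used during surgery, so each subject arguably receives a pharmaceutical product, and 6.1 sets no start time. This makes the definition ambiguous. It does not make it adequate, because capture would then turn on interpretation.
- Patients are reviewed immediately after surgery, the slit lamp checks graft position at every visit, and anterior segment OCT is done on days 0 and 1. These find lasting effects, not problems already resolved on the table.
- Some of the five items are technical difficulties and need not harm the patient. This is fair, but section 3 itself lists them as complications.

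A reader might infer that all intra-operative complications fall outside the plan and will go uncounted. The first four points show why the documents do not support that.

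A reader might also infer that 6.1 keeps these events from the review board. The only non-serious entry in the 6.2 timelines is for unexpected, related events. Section 3 lists these five among the expected risks, so if non-serious they would have no entry even under a corrected definition.

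**Conclusion.** The concern holds for non-serious intra-operative complications that leave no visible post-operative effect: neither 6.1 nor item 5 clearly requires them to be recorded. On the section 3 rates, at least one of the five complications, of any seriousness, has a chance of about 28% to 60% of occurring in 20 operations. This assumes that all 20 patients are operated on and that rates from an endothelial keratoplasty series carry over to DM transplant, as section 3 expects.

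Two further inferences should be resisted. The first is that the adverse-event total is biased downward by a known amount. The intra-operative rates make up 4.5 of 20.2 percentage points in section 3 (4.5 + 15.7 post-operative), or 22% if nothing overlaps. That is a share of listed background rates, not of this trial's adverse events, and no adverse-event total can be derived from the documents. Under-recording is a risk, not a certainty.

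The second is that full capture would let the trial confirm comparable rates. Section 3 states comparability as an expectation, section 2 sets no safety aim, and 20 operations are too few to test it. The gain from the change is a complete descriptive record.

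**What to change.** 1. **Section 6.1.** Extend the adverse-event definition to any unfavourable medical event in a participant who undergoes the DM transplant procedure or receives a study eyedrop, counted from the start of surgery and regardless of cause.
2. **Section 5, item 5.** Widen it to intra-operative as well as post-operative complications, and name the five intra-operative categories in section 3.
3. **Section 8.2.** Tabulate each category and the number of patients with at least one, over the number operated on, with exact confidence intervals. Label these results descriptive and make no claim of comparability.

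The cost is a few sentences in the protocol and a few CRF lines. The reported event count may rise. The change concerns recording and reporting only and alters no clinical management.
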